9.4 Secondary Analyses for High Risk Cohort

The major secondary aim is assessing the two primary outcomes (i.e. incidence of maternal death or sepsis and incidence of intrapartum/neonatal death or sepsis) in the women at high risk for infection cohort. Analyses for this aim will be the same as that specified in 10.4 but subset only on women that meet the high risk definition prior to randomization.

Analyses will also assess if the treatment effect differs between the HR cohort vs. non-high risk women where non-high risk women comprise all women and their infants in the ITT population that delivered prior to meeting criteria for high risk (i.e. they delivered after < 18 hours of labor and < 8 hours post-rupture of membranes). Specifically, the model for the primary analysis of both the maternal and neonatal primary outcomes will be run including a treatment by risk status interaction term and excluding any data from individuals that meet high risk criteria after randomization.

The exclusion of data from individuals meeting high risk criteria between randomization and delivery is intended to provide the most distinct groups regarding the HR risk cohort to non-high risk women comparison. As this exclusion is based on a post-randomization event, sensitivity analyses will be conducted to examine any treatment group differences in meeting high risk criteria post randomization and if there is a difference, to determine the potential magnitude of impact this difference has on treatment effect.

An exploratory analysis will also be completed that assesses if there is a difference in treatment effect between women randomized prior to high risk classification vs. those randomized after high risk classification. Finally, an exploratory analysis will be conducted that assesses the definition of high risk to determine if there is a broader group of individuals that remain at higher risk of infection and/or are observed to have a greater treatment effect (e.g. prolonged labor [≥ 18 hours] and/or rupture of membranes [≥ 8 hours]).

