1.3 Secondary Specific Aims

The single dose of intrapartum azithromycin prophylaxis (2 g) will be compared to placebo to accomplish the following secondary aims:

- Main Secondary Aim for Women at High-Risk for Infection Cohort:
 - a. To evaluate whether the risk of maternal death or sepsis differs among laboring women with and without high-risk for infection (high risk is defined as women with prolonged labor [≥ 18 hours] and/or prolonged membrane rupture [≥ 8 hours] at time of randomization).
- Other secondary specific Aims:
 - b. To evaluate the effectiveness in reducing the risk of individual components of the primary composite endpoints (i.e., maternal death, maternal sepsis, intrapartum/neonatal death, neonatal sepsis including specifically all-cause neonatal deaths and neonatal deaths due to sepsis).
 - c. To evaluate the effectiveness on the risk of intrapartum/neonatal death or sepsis in infants of laboring women at high-risk for infection because of prolonged labor (≥ 18 hours) and/or prolonged membrane rupture (≥ 8 hours).
 - d. To evaluate the effectiveness on the risk of maternal infections including clinical chorioamnionitis, endometritis, wound infections (perineal or Cesarean), abdominal or pelvic abscess, mastitis/breast abscess or infection, pyelonephritis, pneumonia and other bacterial infections in all laboring women as well as in those at high-risk for infection.
 - e. To evaluate the effectiveness in reducing the use of subsequent maternal antibiotic therapy from randomization to 42 days postpartum for any reason in all laboring women as well as in those at high-risk for infection.
 - f. To compare the use of health care resources. Use of health care resources will be measured in terms of maternal and neonatal duration of hospital stay, unscheduled visits, readmission, and admission to special care units/intensive care units in all laboring women and newborns as well as in those at high-risk for infection.
 - g. To assess maternal GI symptoms (e.g., nausea, vomiting, and diarrhea) and other reported side effects, as well as infant pyloric stenosis and type of culture positive infections

(antimicrobial resistance and maternal and infant microbiome diversity are compared in an ancillary study).

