3.1.2 Secondary Analyses – Women at High Risk for Infection Cohort

The major secondary aim is assessing the two primary outcomes (i.e., incidence of maternal death or sepsis and incidence of intrapartum/neonatal death or sepsis) in the women at high risk for infection cohort. These analyses will also assess if the treatment effect differs between the HR cohort vs. non-high-risk women where non-high-risk women comprise all women and their infants in the ITT population that delivered prior to meeting criteria for high-risk (i.e. they delivered after < 18 hours of labor and < 8 hours post-rupture of membranes relative to time of randomization). Specifically, the model for the primary analysis of both the maternal and neonatal primary outcomes will be run including a treatment by risk status interaction term and excluding any data from individuals that meet high-risk criteria after randomization.

The exclusion of data from individuals meeting high risk criteria between randomization and delivery is intended to provide the most distinct groups regarding the HR risk cohort to non-high-risk women comparison. As this exclusion is based on a post-randomization event, sensitivity analyses will be conducted to examine any treatment group differences in meeting high risk criteria post randomization and if there is a difference, to determine the potential magnitude of impact this difference has on treatment effect. An exploratory analysis will also be completed that assesses if there is a difference in treatment effect between women randomized prior to high-risk classification vs. those randomized after high-risk classification. Finally, an exploratory analysis will be conducted that assesses the definition of high-risk to determine if there is a different cut-off that identifies a group of individuals with a greater treatment effect both in relation to randomization and delivery.

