5. ANALYSIS POPULATIONS

As Treated (i.e. Safety [SAF]) Population

The as-treated population will comprise all randomized participants and their infants who received any study treatment grouped by actual treatment received, irrespective of amount or duration of treatment received. Unless specified otherwise, data for this population will be analyzed as available (i.e. irrespective of protocol deviation occurrence, subsequent study participation termination, or study drug withdrawal).

Intention to Treat (ITT) Population

The primary analysis population will be the ITT population, which will include all randomized participants and their infants. All participants will be assigned to the arm to which they were randomized irrespective of treatment received. Unless specified otherwise, all participants will be included in analyses using this population (with data as available or imputed when specified per

section 7.3 and irrespective of protocol deviation occurrence, subsequent study participation termination, or study drug withdrawal).

High Risk for Infection (HR) Population

The HR sub-group will include all women in the ITT and their infants meeting criteria for being high risk (i.e., prolonged labor [≥ 18 hours] and/or rupture of membranes [≥ 8 hours]) at the time of randomization. All participants will be assigned to the arm to which they were randomized irrespective of treatment received. Unless specified otherwise, all participants will be included in analyses using this population (with data as available or imputed when specified per section 7.3 and irrespective of protocol deviation occurrence, subsequent study participation termination, or study drug withdrawal).

Per Protocol (PP) Population

This population will be used to conduct sensitivity analyses for the primary outcome. This population will include randomized participants that received all planned study drug and did not throw up within 15 minutes of taking study drug. Any individuals subsequently identified as ineligible for the study or who were documented as receiving azithromycin during study follow-up excluding study drug will be excluded. Participants will be grouped by actual treatment received. Additional exclusion reasons may be identified after completion of participant enrollment.

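### The high-risk versus non-high-risk interaction excludes women who become high risk after randomization, so its non-high-risk side is selected after dosing, while protocol aim 1.3a fixes risk status at randomization

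*Combined protocol and SAP*

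**What the plan says.** Protocol 1.3, main secondary aim (a), is worded as a comparison by risk group: "To evaluate whether the risk of maternal death or sepsis differs among laboring women with and without high-risk for infection". It fixes status at baseline: "high risk is defined as women with prolonged labor [≥ 18 hours] and/or prolonged membrane rupture [≥ 8 hours] at time of randomization". SAP section 5 defines the HR population in the same way, by status "at the time of randomization. All participants will be assigned to the arm to which they were randomized irrespective of treatment received". SAP 3.2(a) repeats the aim but leaves out the reference to the time of randomization.

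The comparison group in the interaction model is defined differently. SAP 9.4 states that "non-high risk women comprise all women and their infants in the ITT population that delivered prior to meeting criteria for high risk", and the model is run "excluding any data from individuals that meet high risk criteria after randomization". Protocol 3.1.2 has the same rule: "excluding any data from individuals that meet high-risk criteria after randomization". A woman who is not HR at randomization but reaches 18 hours of labor or 8 hours of ruptured membranes before delivery is therefore in neither group.

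Both documents disclose this. They explain that the aim is to make the two risk groups as different as possible, and they add: "As this exclusion is based on a post-randomization event, sensitivity analyses will be conducted". Those analyses look for an arm difference in becoming HR and, where one is found, at how much it affects the treatment effect. A further exploratory analysis compares women randomized before and after HR classification.

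**The concern.** The comparison group is not the complement of the HR group in aim 1.3a. It is what remains of that complement after removing women on the basis of something that happens between randomization and delivery. Protocol 2.3 has the drug given directly after randomization, so the removal follows dosing. Protocol 1.4.2 says that prolonged labor at least doubles infection risk and that prolonged membrane rupture raises it at least two- to three-fold, so the removal is related to the outcome. Protocol 2.5 counts maternal sepsis from randomization, including during labor, so an event can occur before it is known whether the woman will be kept.

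Two things are at stake. The non-HR relative risk, and hence the interaction, is no longer a comparison of randomized groups. And it describes women who can be identified only at delivery, whereas the drug has to be given before then.

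**Working it through.** **The plan's own figure.** The only related calculation in the documents is Table 3 (protocol 3.2.2, SAP 6.2), for the treatment effect within the HR cohort. With p1 = 0.06, p2 = 0.06 × 0.70 = 0.042, mean 0.051, two-sided alpha 0.05 and power 0.85:

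n = [1.960 × √(2 × 0.051 × 0.949) + 1.036 × √(0.06 × 0.94 + 0.042 × 0.958)]² / 0.018² = 2,681 per arm, as printed.

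For 5,500 women, power is 0.852 at 2% loss and 0.848 at 3% loss, against 0.85 stated. That analysis uses status at randomization and is sound on this point. The documents give no sample size or power for the interaction.

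**Inputs for the illustration.**
- From the documents: 34,000 women, 20% HR, HR risk 6%, overall maternal risk 3%, 1:1 allocation, loss 2-3% (3% used).
- Implied non-HR risk: (3% − 20% × 6%) / 80% = 2.25%.
- Evaluable per arm: 34,000 × 0.97 / 2 = 16,490, that is 3,298 HR and 13,192 non-HR.
- Assumed: a share q = 10-20% of non-HR women convert; converters have twice the risk of non-converters; relative risk (RR) 0.70 in HR and 0.85 in non-HR women.

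**Events dropped.** The converters' share of non-HR events is 2q / (1 + q): 0.2/1.1 = 18% and 0.4/1.2 = 33%. Of 34,000 × 80% = 27,200 non-HR women, 2,720 to 5,440 are removed. Risk among those kept is 2.25% / (1 + q), or 2.05% to 1.88%.

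**Precision.** The variance of each log RR is the sum over arms of (1 − p) / (np); the interaction variance is the sum over the two risk groups.

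| | Non-HR log-RR SE | HR log-RR SE | Interaction SE | Power, 0.70 vs 0.85 |
|---|---|---|---|---|
| Nobody excluded | 0.085 | 0.108 | 0.137 | 29% |
| q = 10% excluded | 0.094 | 0.108 | 0.143 | 27% |
| q = 20% excluded | 0.104 | 0.108 | 0.150 | 25% |

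The non-HR standard error rises by 11-23% and the interaction standard error by 4-9%.

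**Bias when treatment changes conversion.** Suppose azithromycin reduces conversion by a fraction f. The women who no longer convert stay in the azithromycin arm with twice the risk, and the observed RR is 0.85 × (1 − q + 2qf) / (1 − q + qf).
- q = 10%, f = 5%: 0.85 × 0.910/0.905 = 0.855.
- q = 20%, f = 10%: 0.85 × 0.840/0.820 = 0.871.

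With no true effect, q = 20%, f = 10% and a converter risk of 4-6%, the same mechanism gives a spurious RR of 1.03-1.09. If azithromycin raised conversion, the bias would go the other way.

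**Bias when conversion rates are equal.** Let 15% convert in each arm. Let a share d of women convert only on placebo (risk 6%) and an equal share only on azithromycin (risk 2.25%). The other converters have risk 6%, overall risk is 2.25%, and treatment has no effect on the outcome.
- d = 1%: the risk in women who convert in neither arm is (0.0225 − 0.15 × 0.06 − 0.01 × 0.0225) / 0.84 = 1.58%. Retained risk is 1.588% on placebo and 1.632% on azithromycin, RR 1.03.
- d = 3%: 1.588% and 1.721%, RR 1.08.

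A check limited to whether conversion rates differ would find nothing in either case.

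**The case against.** Several points on the other side are right. SAP 9.4 opens the major secondary aim with the treatment effect within the HR cohort; protocol 3.2.2 calls that the primary objective of the HR component and sizes 5,500 women for it. A reader might infer that the main secondary aim as a whole rests on a selected set. It does not: the HR group is fixed at randomization and analyzed as randomized, and only the non-HR side and the interaction are affected.

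A reader might also infer that the SAP departed from the protocol, or that the exclusion went unacknowledged. Neither is so. SAP 9.4 follows protocol 3.1.2; the tension lies inside the protocol, between 1.3 and 3.1.2. Aim 1.3a does not itself spell out the comparison group, and the exclusion is stated, explained and given sensitivity analyses.

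It is fair, too, that the illustrated effects are modest, that no interaction power is claimed, and that the interaction has low power under either definition.

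What these points do not answer is the selection itself. The promised assessment of impact goes ahead only when the arms are seen to differ in conversion, with no stated criterion or method, and equal conversion does not exclude bias. The exploratory analysis by timing of HR classification may be the baseline-defined comparison, but its wording could also cover only women who become HR at some point.

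**Conclusion.** The point holds for the interaction and the non-HR treatment effect. As specified, both depend on a post-dosing selection related to infection risk and differ from the baseline definition in aim 1.3a. The within-HR result stands.

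The size is uncertain, because the documents give no conversion rate, no risk for converters and no effect of azithromycin on labor or rupture duration. Over the assumed ranges the loss of precision is modest and the distortion of the non-HR RR is about 0.005 to 0.021 on a true 0.85. It grows with more conversion or a higher converter risk, and could be negligible if conversion is rare. The figures do not support saying that the planned analysis would reverse a conclusion. The case for change is that a comparison protected by randomization is available from the same data and answers the aim as written.

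**What to change.** - Make the main interaction analysis for aim 1.3a the treatment-by-risk-status model with status at randomization: HR at randomization against all other ITT women, nobody excluded.
- Report the version that excludes converters as a sensitivity analysis, whether or not conversion differs between arms.
- Align protocol 3.1.2 and SAP 9.4 with aim 1.3a, by protocol amendment or by an entry in SAP section 12, and restore the timing of risk status in SAP 3.2(a).
- State whether the exploratory analysis by timing of HR classification covers all ITT women or only those who become HR.

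No new data are needed. The cost is slightly less contrast between the two risk groups and a documented change from protocol 3.1.2; a change to SAP wording alone would leave the protocol inconsistent.

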9.5 Secondary Outcome Analyses

Binary secondary outcomes (e.g. individual components of the primary outcome, all other infection indicators, use of antibiotics, maternal and neonatal readmission as well as admission special care unit, maternal GI symptoms, and pyloric stenosis) will be analyzed in a similar manner to the primary analysis of the primary outcomes. Models will be focused on providing estimates of relative risk and associated confidence intervals as opposed to being used for formal tests of hypothesis. If regional differences are observed for the primary outcome, then region-specific models for all secondary outcomes will be run in order to get region-specific estimates of relative risk.

For secondary publications, secondary outcomes may also be explored using additional exploratory models including individually: 1) a treatment by site interaction term, 2) any other antibiotic use during labor (yes or no) and its interaction with treatment, and 3) mode of delivery (cesarean or vaginal) and its interaction with treatment. If the interaction term for any of these models has a $p < 0.1$, then effects will also be reported by the relevant subgroups. These exploratory secondary models will also include any demographic or clinical variables found to differ significantly between the treatment arms in the preliminary analyses described above. From each final model, adjusted relative risk estimates for treatment will be obtained.

For the outcome of time from drug administration until initial discharge after delivery and the outcome of neonatal initial hospital length of stay, the same analysis steps will be employed but using models appropriate for the distribution of these variables (Brock 2011). Specifically, Kaplan-Meier survival curves will be fit to the data in order to get cumulative incidence curves by treatment group of hospital discharge, obtained by treating in-hospital mortality as a competing risk.

10. SAFETY ANALYSIS:

No formal safety analyses are planned as a part of this study, although SAEs and side effects will be summarized. No formal hypothesis tests will be conducted, but descriptive p-values generated using Cochran-Mantel-Haenszel statistics with stratification by GN site will be generated.

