3.1 Statistical Analysis Plan

3.1.1 Primary Analyses

Incidence of maternal death or sepsis and intrapartum/neonatal death or sepsis will be compared between the two treatment arms using generalized linear models. These generalized linear models will be fit with each binary outcome separately as the outcome measure. Estimates of relative risk and associated 95% confidence intervals will be reported. The model will include terms for treatment and site. As randomization occurs at the pregnancy level and approximately 1-2% of pregnancies are anticipated to be multiple gestations, models for neonatal outcomes will account for correlation among multiples assuming an exchangeable covariance structure. For the two primary outcomes, these analyses will be conducted using the ITT population and the p-values associated with the treatment term will be used to formally test each of the two primary hypotheses at the alpha = 0.05 level.

As secondary analyses of the primary outcomes, assuming an overall treatment effect is observed, the models will be run including region (Africa, Latin America, or Asia) and a treatment by region interaction

term. If the interaction term has a $p < 0.1$, then effects will be reported by region with treatment effect within region tested at the 0.025 level.

Additional exploratory models will also be run including individually: 1) a treatment by site interaction term, 2) any other antibiotic use during labor (yes or no) and its interaction with treatment, and 3) mode of delivery (cesarean or vaginal) and its interaction with treatment. If the interaction term for any of these models has a $p < 0.1$, then effects will also be reported by the relevant subgroups. These exploratory secondary models will also include any demographic or clinical variables found to differ significantly between the treatment arms in the preliminary analyses described above.

From each final model, estimates of relative risk associated with treatment will be obtained including unadjusted estimates of risk from the primary model as well as estimates of risk adjusted for potential confounders from the secondary analyses.

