3.1.3 Secondary Analyses – Other Secondary Outcomes

Other maternal and neonatal binary outcomes including: the individual components of the primary outcomes, neonatal deaths due to sepsis, maternal infections (clinical chorioamnionitis, endometritis, wound infections (perineal or subsequent cesarean), pyelonephritis and pneumonia), use of subsequent maternal antibiotic therapy, pyloric stenosis and occurrences of maternal or neonatal readmission or admission into special care unit will be analyzed using the approaches detailed in **Section 3.1.1** for the ITT population and approaches detailed in **Section 3.1.2** for the HR cohort. A similar process with generalized linear models employing an appropriate link function will be used to analyze the outcomes of maternal and neonatal initial hospital length of stay.

Binary safety outcomes, e.g., nausea, vomiting, and diarrhea, will also be analyzed using the approaches detailed in **Section 3.1.1**. These analyses will be conducted using the As Treated population.

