7. STATISTICAL / ANALYTICAL ISSUES

7.1 General Rules

All statistical computations will be performed and data summaries will be created using SAS 9.3 or higher. If additional statistical packages are required, these will be discussed in the study report. For summaries of study data, categorical measures will be summarized in tables listing the frequency and the percentage of participants in each study arm; continuous data will be summarized by presenting mean, standard deviation, median, minimum, and maximum; and ordinal data will be summarized by presenting median and the limits of the interquartile range.

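### SAP 10 gives no effect estimate or confidence interval for SAEs and named harms not modelled under SAP 9.5, although the protocol plans relative risks with 95% CIs for binary safety outcomes

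*Combined protocol and SAP*

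**What the plan says.** **Protocol.** Section 3.1.3 states: "Binary safety outcomes, e.g., nausea, vomiting, and diarrhea, will also be analyzed using the approaches detailed in" Section 3.1.1, and "These analyses will be conducted using the As Treated population". Section 3.1.1 fits a generalized linear model with treatment and site, and "Estimates of relative risk and associated 95% confidence intervals will be reported". Section 2.8 names anaphylaxis, allergic reactions (rash), liver failure and arrhythmias as azithromycin risks and has them reported as serious adverse events.

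**SAP.**
- Section 10 opens: "No formal safety analyses are planned as a part of this study, although SAEs and side effects will be summarized". It continues: "No formal hypothesis tests will be conducted, but descriptive p-values generated using Cochran-Mantel-Haenszel statistics with stratification by GN site will be generated".
- Section 7.1 fixes what a summary of a categorical measure contains: "categorical measures will be summarized in tables listing the frequency and the percentage of participants in each study arm".
- Section 7.5 labels safety p-values as descriptive.
- Section 9.5 keeps the modelling approach for a list of binary outcomes that ends with "maternal GI symptoms, and pyloric stenosis) will be analyzed in a similar manner to the primary analysis of the primary outcomes". The list also includes the components of the primary outcomes (hence deaths), readmission and special-care admission. The section says its models aim at relative risks and intervals rather than tests.
- Section 12, reserved for changes from the protocol's analyses, shows only a heading in the text available.

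**The concern.** SAEs of the kinds listed in protocol 2.8 fall under SAP 10, where the only comparative statistic named is a p-value. These harms are expected to be rare. A p-value from a handful of events does not tell the reader how large an excess remains compatible with the data, which is what a safety table for a prophylactic dose should show. Protocol 1.6.3 and 3.5.5 discuss a regulatory advisory on arrhythmia, and protocol 3.6.4 plans to seek guideline change if results are positive. The range of harm ruled out by 34,000 women is therefore a result that readers will want.

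The SAP is also uneven. Sections 9.5 and 10 both disclaim formal testing, but 9.5 turns to estimates and intervals while 10 turns to p-values.

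**Working it through.** **1. Which outcomes are left without an interval**

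| Outcome | Where analysed in the SAP | RR and CI? |
|---|---|---|
| Maternal, intrapartum/neonatal and all-cause neonatal death | 9.2, 9.5 (ITT and As Treated) | Yes |
| Readmission, special-care admission | 9.2, 9.5 (ITT) | Yes |
| Maternal GI symptoms, including mechanistically related AEs such as abdominal pain | 9.2, 9.5 (As Treated) | Yes |
| Pyloric stenosis | 9.2, 9.5 (As Treated) | Yes |
| Non-fatal arrhythmia, anaphylaxis, liver failure, rash; other SAE categories | 10 (no population named) | No: counts, percentages, CMH p-value |

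**2. Arm size.** The documents state no figure for the safety analysis. The total is 34,000 at 1:1 (SAP 6.1 and 4.3), so N = 17,000 per arm. As a check on the design inputs, the pooled-variance two-proportion formula for 3% versus 2.4%, two-sided alpha 0.05 and 90% power gives 15,334 per arm, as in SAP Table 1.

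**3. What a p-value shows with few events.** Assume 6 versus 3 events (a = 6, b = 3, m = 9). Site counts are not given, so one pooled stratum is used.
- CMH without continuity correction: (a − m/2)² / V, where V = m(2N − m)N² / [(2N)²(2N − 1)] = 2.249. This gives 1.5² / 2.249 = 1.00, p = 0.32.
- RR = 6/3 = 2.0.
- Exact conditional 95% CI: given m, a is binomial with probability RR/(1 + RR). The Clopper-Pearson limits for 6/9 are 0.299 and 0.925. Converting by p/(1 − p) gives RR limits of 0.43 and 12.4.
- Risk difference: 3/17,000 = 1.8 per 10,000, Newcombe 95% CI −2.2 to 6.1 per 10,000.

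The p-value conveys none of this range. With 0 events in 17,000, the upper limit of the exact two-sided 95% interval is 1 − 0.025^(1/17,000) = 2.2 per 10,000, which is informative and needs no test.

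**4. Power at plausible rarity (placebo risks assumed).** With the same two-proportion method at 17,000 per arm and a placebo risk of 1 per 10,000, power is about 11% for a doubling and 26% for a tripling. At 5 per 10,000, power for a tripling is about 83%. Non-significance is therefore weak evidence at the rarer end.

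**5. Why the modelled RR needs a sparse-data rule.** A relative-risk (log-link) model has no finite treatment RR when one arm has no events. Under RR = 1 and 1:1 allocation:
- Exactly k events: 2 × 0.5^k, which is 12.5% for k = 4 and 1.6% for k = 7.
- Expected total of k (Poisson, mean k/2 per arm): 2e^(−k/2) − e^(−k), which is 25% for k = 4 and 6% for k = 7. This includes trials with no events at all.

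The fallback in SAP 9.3 for convergence trouble drops the correlation among multiples. That does not help with an empty arm.

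**The case against.** The strongest reply is that SAP 10 does not leave the reader with p-values only. Counts and percentages by arm are planned under SAP 7.1, so anyone can compute a crude interval. That stands. A reader might infer from SAP 10 that rare harms can only ever be reported as not significant; the documents do not support this. The p-values are marked descriptive, and a lopsided split can fall below 0.05: at 17,000 per arm, 6 versus 0 gives a CMH p of 0.014 and 4 versus 0 gives 0.045. The 4 versus 0 case also has a Fisher p of 0.125 and an exact lower RR limit of 0.66, so the CMH p-value is itself fragile with so few events.

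Second, a reader might infer that the SAP has discarded the protocol's plan for all safety outcomes. It has not. The protocol's examples are nausea, vomiting and diarrhea, which keep an RR and CI through SAP 9.5, as do deaths, readmission and pyloric stenosis. Protocol 3.1.3 does not name SAEs, so applying it to each SAE type is a reading, though a natural one for binary harms.

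Third, a site-stratified method for sparse events is arguably more suitable than the protocol's regression model. That is fair: what is missing is an interval, not that particular model.

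Fourth, SAP 5 calls the As Treated set the safety population, so its use in section 10 is probably intended. Section 10 should still say so.

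Finally, SAEs are assessed individually for relatedness and reviewed by the DMC. That protects participants but does not supply the comparative estimate for the report. Crude intervals worked out by readers would ignore site, and the method would not be pre-specified.

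**Conclusion.** The point holds in a limited form. For SAEs and named harms outside the SAP 9.5 outcomes, SAP 10 specifies no estimate, interval or population. The protocol's approach to binary safety outcomes was a relative risk with 95% CI in the As Treated population, and SAP 12 shows no record of the change. The practical loss is that the excess of harm ruled out by the trial is not reported: in the 6 versus 3 example, p = 0.32 accompanies an interval that reaches a twelve-fold excess.

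The event counts and placebo risks are assumptions, since the documents give no trial rates for these harms. The calculations pool over sites and use the planned 17,000 per arm. This is a worthwhile improvement of low severity; no primary conclusion depends on it.

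**What to change.** - **SAP 10:** for each SAE category and each harm named in protocol 2.8, report the site-stratified Mantel-Haenszel relative risk and risk difference with 95% CIs, and state that the As Treated population is used. The descriptive p-values may stay beside them; removing them would be a matter of preference.
- **SAP 9.5 and 10:** when either arm has fewer than 5 events, use an exact site-stratified conditional interval for the relative risk.
- **SAP 12:** record the departure from protocol 3.1.3 and the reason for it.

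The cost is some table programming, and intervals for the rarest events will be visibly wide or have no finite upper limit. No additional data collection is required.
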